Stress and Anxiety Measures. Stress and anxiety levels will be assessed using the **HAM-A**⁵⁵, **PSS**⁵⁶, **BDI-II**, and the **PCL-5**. Established norms will be used for the HAM-A and PSS to assess mild to moderate stress and anxiety and screen out for cases of severe stress and anxiety.

Stress Reactivity Measures. HR and BP will be assessed using standard laboratory equipment. Saliva samples will be collected in swabs using the Cortisol-Salivette® system (Sarstedt) and measured using the Cortisol ELISA Kit (Enzo Life Sciences), per manufacture instructions.

Study Medication. Pioglitazone (Actos®, Takeda Pharmaceuticals U.S.A., Inc.) is FDA-approved for the treatment of diabetes mellitus type 2; has anti-inflammatory, neuroprotective, antioxidative, and anti-excitotoxic properties⁷²; and extensive research has shown it to be safe in human patient populations^{73,74}. The medication schedule is based on previous work from our group showing that a daily dose of 45mg was associated with acceptable levels of tolerability, safety, and compliance in a study assessing the effects of pioglitazone on individuals with CUD and AUD²⁷. Our pilot trial used a conservative 2-week dose titration schedule (i.e., Week 1: 15 mg/d; Week 2: 30 mg/d), with no adverse effects reported or observed. For the current trial we will follow recommended adult initial dosing at 30 mg/d to reach maintenance dose of 45 mg/d by week 2, which is within standard titration parameters as per the investigator's brochure. Thorough screening of all subjects including history and physical examination, serum chemistry and hematology, EKG, urinalysis and Urine Drug Screen as well as structured psychiatric interviews will be completed on all subjects. Exclusion criteria include subjects at greatest risk of side effects of pioglitazone, including those with congestive heart failure, significant liver disease, edema, and diabetes, as well as risks of alcohol use (pregnant

women). Monitoring of weight to capture potential fluid retention will occur at each visit along with an adverse event assessment to include assessment for edema. Blood will be drawn at the end of the study for liver function testing. Female subjects must agree to use an effective barrier method of birth control and urine pregnancy tests will be performed at each visit to minimize risk of pregnancy.

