Medication Compliance. One week supplies of the study medication will be dispensed with a Medication Event Monitoring System (MEMS) cap to record the number of bottle openings and date/time of each opening. Riboflavin will be added to medication capsules and urine ultraviolet fluorescent tests will be conducted at weekly clinic visits to assess compliance. Participants will receive \$10 at each clinic visit in which results from self-report, MEMS, and riboflavin are all consistent with medication compliance.

Human Laboratory Procedures (Specific Aim 1). On Study Weeks 0 and 4, participants will engage in the cold-pressor task (CPT). The CPT is widely used as a stress-inducer in human laboratory studies and elicits moderate activation of the sympathetic nervous system and limited activation of the HPA-axis, which are two major stress systems in the body⁷⁵⁻⁷⁸. HPA-axis activation during the CPT can be increased by incorporating a social evaluative component. Specifically, a study member of the opposite sex of the study participant will dress in a white labcoat and be physically present during the CPT. Additionally, participants will be videotaped and informed that their facial expressions will be assessed during the CPT. The addition of the social component during the CPT has been demonstrated to selectively activate the HPA-axis and significantly increase salivary cortisol levels⁷⁷. During the CPT, participants will submerge their dominant arm in an ice-water bath for up to 2 minutes. Stress levels will be assessed using subjective and physiological measures HR, BP, and salivary cortisol consistent with previous studies from our group^{79,80}. Alcohol craving will be assessed using a 4-item questionnaire⁵⁷.

Table 2. Time Course for Assessing Stress-Induced Relapse Risk

Time (pm)	Study Procedures
3:00	Assess Craving, BAAD, Stress, Cortisol, HR, BP
3:15	Cold Pressor Task
3:20	Assess Craving, BAAD, Stress, HR, BP
3:45	Assess Craving, BAAD, Stress, Cortisol, HR, BP

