Natural Environment Procedures (Specific Aim 2). At Study Week 0, all participants will receive a pamphlet copy of the “Rethinking Drinking: Alcohol and Your Health” providing research-based information related to alcohol use (RethinkingDrinking.niaaa.nih.gov). Research staff will go over the pamphlet’s information with the participant at the initial visit and subsequent visits as necessary. At each study visit, participants will receive study medication for the week and assessed for adverse events and medication compliance. At each visit, participants will also be assessed for recent alcohol use (self-report, ETG, BrAC), alcohol craving (PACS), and stress/anxiety (HAM-A, PSS). At the end of the study, participants will be referred to local alcohol treatment services as needed.

Participant Payment & Compensation. Participants will receive be able to receive \$300 for completing the study (\$50 for completing baseline screening; \$25 for each visit (\$100); \$25 for stress reactivity assessments (\$50); and \$100 completion bonus). Additionally, participants will potentially receive \$10/week (up to \$40) for demonstrating medication compliance. Participants will also receive parking/bus fare compensation at each visit worth \$5.

DATA ANALYSIS PLAN

General Data Analytic Strategy. Analyses will proceed in parallel using frequentist and Bayesian statistical inference. Frequentist analyses will examine relationships between predictors and outcomes using traditional measures of effect size and statistical significance (i.e., regression coefficients, standard errors,

confidence intervals, and p -values), while Bayesian analyses will measure uncertainty in model parameter estimates via posterior distributions and directly evaluate the probability of the alternative hypothesis.

Specific Aim 1: assess pre- to post-treatment reductions in stress reactivity (self-report, salivary cortisol, heart rate, blood pressure) and stress-induced alcohol craving (self-report, alcohol demand) in the human laboratory setting.

Hypothesis 1: We will observe pre- to post- treatment reductions in stress reactivity and stress-induced alcohol craving. Generalized linear mixed modeling will be used to evaluate each outcome as a function of time (pre-test and post-test) in unique models.

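### Table 2 schedules no heart rate or blood pressure reading during the cold-pressor immersion, so the Aim 1 cardiovascular reactivity outcomes may miss part of the response and partly reflect recovery

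*Combined protocol and SAP*

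**What the plan says.** Under METHODS, Human Laboratory Procedures (Specific Aim 1), participants undergo the "cold-pressor task" at Study Weeks 0 and 4. The protocol says that the task "elicits moderate activation of the sympathetic nervous system" and has a more limited effect on the HPA axis, which the social-evaluative component is meant to strengthen. On exposure, "participants will submerge their dominant arm in an ice-water bath for up to 2 minutes".

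Table 2 gives the session clock:

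- 3:00 pm: "Assess Craving, BAAD, Stress, Cortisol, HR, BP"
- 3:15 pm: the task, with no measurement listed
- 3:20 pm: "Assess Craving, BAAD, Stress, HR, BP"
- 3:45 pm: the same list as at 3:00

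On measurement, the same section says "Stress levels will be assessed using subjective and physiological measures HR, BP, and salivary cortisol", in line with earlier work by the group. The Stress Reactivity Measures paragraph adds only that "HR and BP will be assessed using standard laboratory equipment". Neither mentions continuous recording or a reading during the task.

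The DATA ANALYSIS PLAN for Specific Aim 1 names the outcomes as "stress reactivity (self-report, salivary cortisol, heart rate, blood pressure", followed by stress-induced craving. Each is modelled as a function of time, meaning pre-test versus post-test. It does not say which reading within a session, or which change score, is the reactivity outcome.

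**The concern.** The task is chosen partly because it activates the sympathetic system, and HR and BP are the plan's only cardiovascular measures of that activation. Followed as written, the schedule takes neither while the stressor is on.

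Two things are at stake. First, Hypothesis 1 needs a response at Week 0 that can shrink by Week 4. Whatever part of the HR/BP rise has gone by 3:20 cannot contribute to a pre-to-post reduction, and the estimated effect is diluted. The study is meant to supply preliminary data for a grant application and effect sizes for later power calculations, so a diluted estimate would carry forward.

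Second, participants may withdraw early. Immersion time sets both how much stressor they receive and how long after it they are read. If tolerance changes between Weeks 0 and 4, the HR/BP result can change with no change in reactivity. Immersion time is not listed among the data to be recorded.

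**Working it through.** The plan states no figure for this point, so there is none to reproduce. Its power statement concerns alcohol consumption and is not an input.

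**Step 1: lag from the clock.** Inputs from Table 2 and the task description: task at 3:15, immersion of at most 2 minutes, next HR/BP reading at 3:20.

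Lag = 3:20 − (3:15 + start delay + immersion time)

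| Start delay (min; values above 0 are assumed) | Immersion 2 min | 1 min | 0.5 min |
|---|---|---|---|
| 0 | 3 | 4 | 4.5 |
| 1 | 2 | 3 | 3.5 |
| 2 | 1 | 2 | 2.5 |
| 3 | 0 | 1 | 1.5 |

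With no delay the lag runs from 3 minutes (full immersion) to just under 5 (almost immediate withdrawal). The 3:45 reading comes 28 minutes after a full immersion that began at 3:15. In no row is there a reading during immersion.

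**Step 2: share of the response left.** The documents give no recovery rate, so I assume exponential recovery over a range of half-lives.

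Share left = 0.5^(lag / half-life)

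| Assumed half-life (min) | 1-min lag | 3-min lag | 4.5-min lag |
|---|---|---|---|
| 0.5 | 25% | 2% | 0.2% |
| 1 | 50% | 13% | 4% |
| 2 | 71% | 35% | 21% |
| 5 | 87% | 66% | 54% |

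**Step 3: effect of a change in tolerance.** Suppose a participant stays in for 2 minutes at Week 0 and 1 minute at Week 4, with the same peak response. The lag goes from 3 to 4 minutes. At a 2-minute half-life the share left goes from 35% to 25%, a ratio of 0.5^(1/2) = 0.71. That is an apparent fall of about 29% with no change in peak reactivity. The opposite change in tolerance would hide a real fall. The documents do not say how often tolerance changes.

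**Step 4: illustrative power.** Assume a true pre-to-post effect of 0.6 SD on the peak, n = 20, a one-sided paired t test at 0.05 and unchanged noise. Power from the noncentral t distribution is 83% at the peak. With the effect at 3:20 equal to 0.6 × share left:

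| Half-life (min) | Effect at 3-min lag (SD) | Power, 3-min lag | Power, 1-min lag |
|---|---|---|---|
| 0.5 | 0.6 × 0.016 = 0.009 | 5% | 16% |
| 1 | 0.6 × 0.125 = 0.075 | 9% | 36% |
| 2 | 0.6 × 0.354 = 0.212 | 23% | 57% |
| 5 | 0.6 × 0.66 = 0.396 | 53% | 73% |

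Unchanged noise is the harshest choice. If half the variance of the pre-to-post change is person-to-person variation in response, that half shrinks with the response, and the effect becomes 0.6 × share / √(0.5 + 0.5 × share²). At a 3-minute lag this gives 0.212 / √0.5625 = 0.283 SD and about 34% power for a 2-minute half-life, and about 64% for 5 minutes.

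**The case against.** A reader might infer three stronger statements. The documents support none of them.

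- **That HR and BP are never read during the task.** The documents are silent on this; they do not exclude it. The text refers to the group's earlier studies and to standard equipment, either of which could involve in-task recording. What can be said is that Table 2 schedules none. Table 2 is nevertheless the stated time course and names HR and BP in every row except the task row. If in-task recording is intended, the plan should say so and say which value is analysed.
- **That the first reading is at least 3 minutes late.** This needs the arm to enter the water at exactly 3:15. The task also involves an observer, videotaping and an instruction about facial expressions. If these take 1, 2 or 3 minutes of that slot, a full immersion ends 2, 1 or 0 minutes before 3:20. The lag is then shorter, but it is also uncontrolled, and there is still no reading during immersion. The questionnaires precede HR and BP in the 3:20 row, but the list is not stated to be an order of administration.
- **That these outcomes measure recovery instead of the stress response.** This needs a recovery rate. At a 5-minute half-life, 66% of the response is still present at 3 minutes, so the 3:20 reading would hold most of it.

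Two further points stand and limit the stakes. HR and BP are two of four reactivity measures in a pilot of 20, and the schedule also serves self-reported stress, craving, alcohol demand and cortisol, which this point does not affect. No power claim for HR or BP is made, so none is undermined. A post-task reading is also partly a design choice, and a cuff inflation could intrude slightly on the stressor.

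**Conclusion.** The concern holds in a limited form. Table 2 schedules no HR or BP reading during immersion. The first later reading is nominally 3 to 5 minutes after withdrawal, less if set-up delays the start, and the lag varies with tolerance at each session. The Aim 1 HR and BP outcomes may therefore miss part of the response and partly reflect recovery.

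The size of the loss is unknown. The 2% to 66% range at 3 minutes rests on assumed exponential recovery with half-lives of 0.5 to 5 minutes, and nothing in the documents selects a value within it. The power figures are illustrative only, because they also assume a 0.6 SD effect and unchanged noise.

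This is more than a missing detail: following the written schedule yields no cardiovascular reading while the stressor is on. The change is worth making before data collection. Confidence is medium.

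**What to change.** 1. In Table 2, add one HR and BP reading during immersion at Weeks 0 and 4, using the equipment already in place, at a stated point relative to the start of immersion.
2. In the Aim 1 analysis text, define HR and BP reactivity as that reading minus the 3:00 value.
3. Keep 3:20 and 3:45 as post-stress points, and state that HR and BP are taken before the questionnaires.
4. Record the start and duration of immersion at both sessions, and report them beside the reactivity result.
5. If in-task recording is already intended, state this in Table 2 and name the value to be analysed.

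The cost is one extra reading in each of two existing sessions, at most 20 × 2 = 40 readings in all, plus a small change to the session form. It adds no visits. The downside is one cuff inflation during the task in each session; because it occurs at both Week 0 and Week 4, it is common to both sides of the comparison.

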The primary purpose of the current proposal is to obtain preliminary data to increase the likelihood of funding for a future NIH grant, while balancing the feasibility of completing the current proposal. To that end, we will utilize a within-subject, repeated measures design to assess the feasibility of administering pioglitazone for four weeks to non-treatment and treatment-seeking individuals with AUD and elevated levels of stress/anxiety (**N=20**). Participants will undergo pre- and post-treatment human laboratory assessment of stress-reactivity and stress-induced alcohol craving. During treatment, changes in alcohol use, stress/anxiety, and alcohol craving will be assessed in the natural environment. The study design features 1) rigorous monitoring of medication compliance (Medication Event Monitoring System (MEMs)) and alcohol use (urinary ethyl glucuronide (ETG)); 2) biological assessment of stress reactivity (salivary cortisol, blood pressure, and heart rate); and 3) a multi-dimensional assessment of stress-induced alcohol craving incorporating both traditional measures of alcohol craving in addition to relatively novel behavioral economic measures (delay discounting, alcohol demand). Taking these measures together, we hope to present a robust and comprehensive characterization of pioglitazone on alcohol use, stress reactivity, and stress-induced alcohol craving.

SPECIFIC AIMS

Specific Aim 1: To assess pre- to post-treatment reductions in stress reactivity (self-report, salivary cortisol, heart rate, blood pressure) and stress-induced alcohol craving (self-report, alcohol demand) in the human laboratory setting.

Hypothesis 1: *We will observe pre- to post- treatment reductions in stress reactivity and stress-induced alcohol craving.*

Specific Aim 2: To assess changes in alcohol drinking (drinks per day, heavy drinking days), stress/anxiety (PSS, HAMA, PCL-5), and alcohol craving (PACS, delay discounting, alcohol demand) during treatment in the natural environmental setting.

Hypothesis 2: *We will observe decreased alcohol drinking, stress/anxiety, and alcohol craving over the course of treatment.*

There is increasing attention and evidence supporting the potential role of the PPAR γ system as a novel target in the treatment of AUD. From a translational perspective, this study is timely and likely to advance our understanding of stress as a mechanism of action of pioglitazone effects.

IRB NUMBER: HSC-MS-18-0922

BACKGROUND AND RATIONALE

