and predict alcohol treatment response³⁹⁻⁴². Delay discounting and alcohol demand are poorly correlated with each other, supporting a multi-dimensional model in which these measures represent distinct aspects of motivation to use alcohol⁴²⁻⁴⁸. In the current proposal, we will assess changes in both delay discounting and alcohol demand over Study Weeks 0 to 4 and alcohol demand will be used to assess state-dependent changes during the human laboratory stress-reactivity assessment.

METHODS

Research team. The research team will consist of [name] (PI) and a number of collaborators from UTHealth and Brown University. [name] (PI) is an experienced addiction researcher and an expert in assessing behavioral economic measures in addiction research, which is pertinent to the current project. Drs. [name] (CNRA Medical Director) and [name] (Addictions Psychiatrist) will provide medical guidance and ensure participant safety over the course of the study. [name] is Professor and Vice Chair for Research and directs the Behavioral Laboratory at the CNRA with expertise in medication development trials as well as alcohol studies. [name] is a biostatistician and data scientist with expertise in experimental design and statistical modeling, including the type of generalized linear modeling that will be utilized by the present research. From Brown University, [name] (Co-I) is serving as a consultant on this project and is an expert in stress and alcohol research¹⁻⁷. Additionally, our group has a history of collaborating with the Laboratory of Biomarkers located in the BBSB for analyzing biological samples, such as salivary cortisol in the current protocol. We will work with [name] to ensure that samples are collected and analyzed appropriately.

Overall study design. We will utilize a within-subject, repeated measures design. Participants will receive pioglitazone or placebo for four weeks. A summary of the study timeline, procedures, and assessments is shown in the following Table.

Table 1. Outline of Study Timeline, Procedures, and Assessments

Study Week Procedures and Assessments	0	1	2	3	4
Consent and Baseline Screening SCID, ASI, KMSK, TLFB, CIWAA, AUDIT	X				
Receive Study Medication (Pioglitazone or Placebo) Assess Medication Compliance and Adverse Events	X	X	X	X	X
Human Laboratory Procedures (Specific Aim 1) Stress-Reactivity Assessment (Salivary Cortisol, HR, BP, Craving) Alcohol Demand, Alcohol Ladder	X				X

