Specific Aim 2: Demonstrate reduced alcohol drinking (drinks per day, heavy drinking days), stress/anxiety (PSS, HAMA, PCL-5), and alcohol craving (PACS, delay discounting, alcohol demand) during treatment in the natural environmental setting.

Hypothesis 2: We will observe decreased alcohol drinking, stress/anxiety, and alcohol craving over the course of treatment. Generalized linear mixed modeling will be used to evaluate each outcome as a function of time in unique models. Alcohol consumption will be modeled via drinks per drinking day, such that the number of positive drinking episodes a participant experienced in a week will be included as a count outcome (i.e., Poisson-distributed) and the number of drinking days in a week will be controlled for as an off-set covariate.

Power/Sample Size Considerations. The frequentist framework using null hypothesis statistical testing can provide some understanding of changes over time for each outcome. However, in evaluating a small within-subjects pilot trial of $N = 20$ participants, Bayesian statistical inference provides a superior framework for deriving evidence regarding the magnitude and direction of change over time for each model. The posterior probability of each effect would then be useful to inform effect sizes for power calculations and/or prior distributions in future research. As due diligence, however, a conventional frequentist power analysis follows. For the current proposal, power estimates are calculated using G*Power 3.1.9.2 and focus on reduction in alcohol consumption. Assuming alpha = 0.05 (one-tailed), an average baseline rate of 10.5 drinks/week across all participants (averaged between 14 and 7 drinks/week for male and female participants, respectively), a sample size of $N = 20$ participants provides 80% power to detect a 20% decrease in alcohol consumption over five weeks.

REFERENCES

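### Aim 2 change over time combines pioglitazone, alcohol education started in the same study week and other influences, so it cannot be carried forward as a pioglitazone effect

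*Combined protocol and SAP*

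**What the plan says.** All places are in the combined protocol and SAP.

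- **Education** (Methods, Natural Environment Procedures): "At Study Week 0, all participants will receive a pamphlet copy of the" Rethinking Drinking material. Research staff go through it "with the participant at the initial visit and subsequent visits as necessary". No criterion, length or limit is given for the repeats. Table 1 has no row for education, and no log is described.
- **Medication** (same section): "At each study visit, participants will receive study medication for the week". Table 1 marks medication from Week 0.
- **Design** (Methods, Overall study design): "We will utilize a within-subject, repeated measures design", followed by "Participants will receive pioglitazone or placebo for four weeks". Table 1 repeats the mention of placebo. Randomisation, allocation ratio, blinding and a between-group contrast are not described anywhere. The Abstract speaks only of giving pioglitazone to the 20 participants.
- **Analysis** (Data Analysis Plan, Specific Aim 2): "Generalized linear mixed modeling will be used to evaluate each outcome as a function of time in unique models". The hypothesis reads "We will observe decreased alcohol drinking, stress/anxiety, and alcohol craving over the course of treatment".
- **Intended use**: the Abstract says "we hope to present a robust and comprehensive characterization of pioglitazone on alcohol use, stress reactivity, and stress-induced alcohol craving". The Power/Sample Size section expects the posterior for each effect to feed the effect sizes, power calculations or priors of later research.

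**The concern.** Medication and an intervention aimed directly at drinking begin in the same study week, and the model has one term, time, to describe what follows. There is no treatment term, education covariate, medication-free run-in or education-only period. Any response to the education enters the time coefficient in the hypothesised direction. So do the effects of weekly breath and urine alcohol testing and of regression to the mean, since entry requires excessive past-month drinking and a raised anxiety or stress score.

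The main product of this pilot is an estimate for the next grant. If that estimate is passed on as a pioglitazone effect, a later trial that gives the same education to both arms would be planned on a difference that is too large, and would be underpowered.

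The open-ended repeats add a smaller problem. Drug exposure is tracked by bottle-cap monitor, riboflavin and self-report, but education exposure is not tracked at all. Afterwards nobody could say how much education any participant received.

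**Working it through.** **1. The plan's own figure.** The Power/Sample Size section states 80% power with N = 20, one-tailed alpha 0.05, for a 20% fall from 10.5 drinks/week over five weeks. It does not name the test, the SD, the overdispersion, the within-person correlation or the exposure, so the 80% is not determined by what is given. Variants tried, all with N = 20, rate ratio 0.80 and one-sided 0.05:

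- Poisson regression, balanced binary predictor: 49.0% with 1 week of exposure, 80.5% with 2.5 weeks, 96.8% with 5 weeks.
- Within-person Poisson log-linear trend, Weeks 0-4: 78.0%.
- Within-person Poisson, Week 0 against Weeks 1-4: 88.1%.
- Paired t-test: 80% needs a standardised change of 0.577. For a fall of 0.20 × 10.5 = 2.1 drinks, that means an SD of change of 2.1/0.577 = 3.64, which is not stated.

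The 80% is neither confirmed nor shown wrong.

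**2. What the time coefficient contains.** On the log scale:

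ln(RR total) = ln(RR drug) + ln(RR education) + ln(RR other)

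Only the left side is estimated. Suppose the observed total is the planned 0.80 and RR other is set to 1. Then RR drug = 0.80/(1 − education fall):

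| Assumed education fall | RR drug compatible with a total of 0.80 |
|---|---|
| 5% | 0.80/0.95 = 0.84 |
| 10% | 0.80/0.90 = 0.89 |
| 15% | 0.80/0.85 = 0.94 |
| 20% | 0.80/0.80 = 1.00 |

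The planned data cannot tell these rows apart.

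**3. Illustration: no drug effect, education alone lowers drinking.** The size r of the education fall is an assumption (5-20%), because the documents give none.

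(a) Taking the stated power at face value, the expected test statistic at a 20% fall is 1.645 + 0.842 = 2.487. For a fall r, the chance of declaring a decrease is Φ(2.487 × ln(1−r)/ln(0.8) − 1.645).

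(b) Independent Poisson trend: expected weekly count μ(w) = 10.5(1−r)^(w/4) for w = 0 to 4; information I = 20 × Σ μ(w)(w − w̄)², where w̄ is the μ-weighted mean week; chance = Φ(|ln(1−r)|/4 × √I − 1.645). With overdispersion of 2, I is halved. For r = 10%, I = 1,992, so 0.02634 × √1,992 = 1.176, and Φ(1.176 − 1.645) = 0.32.

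| r | (a) | (b) Poisson | (b) overdispersion 2 |
|---|---|---|---|
| 5% | 14% | 14% | 11% |
| 10% | 32% | 32% | 21% |
| 15% | 57% | 56% | 35% |
| 20% | 80% | 78% | 53% |

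**4. Limit of step 3.** The power statement concerns weekly consumption. The Aim 2 model is for drinks per drinking day, with drinking days as an offset. Education that only reduced the number of drinking days would not move that rate, so these percentages need not apply to the planned test. Step 2 holds for any outcome modelled on time alone.

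**The case against.** **Placebo is mentioned.** With a concurrent placebo group, education offered to everyone would be common background, and a between-arm contrast would largely remove it. That is true of such a contrast, but none is planned. The time-only model would pool any placebo participants with the rest, so the mention does not rescue the analysis. It does mean that the unreconciled comparator is the root problem and has to be settled first.

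**Education is not the only non-drug influence.** This stands. Monitoring, expectancy and regression to the mean sit in the same coefficient. Naming only drug plus education would still be incomplete.

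**Hypothesis 2 claims only a fall over time, and the stated primary purpose is preliminary data.** This also stands, and it limits the point to attribution and onward use. The Abstract nevertheless presents the results as characterising pioglitazone.

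**Three stronger readings are tempting and are not supported.**

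- A reader might infer that drug and education start on the same day. The documents give a study week and an initial visit. Baseline screening is paid separately from the four $25 visits, so the first review and first dispensing need not coincide.
- A reader might infer that repeat sessions follow continued drinking. No criterion is stated; repeats could simply answer questions.
- A reader might set the rates in the illustration against the 5% alpha and call them false positives. If education does lower drinking, rejecting no fall over time is correct for Hypothesis 2 as worded. Only the step from that fall to pioglitazone fails.

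A reader might also think that one fixed education session would solve the problem. It would standardise exposure but leave drug and education confounded with time, and how much support to offer is partly a matter of participant care.

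**Conclusion.** The concern holds as a limit on interpretation. Aim 2 can show whether drinking, stress/anxiety and craving fall during the study. As planned, it cannot show how much of that fall is due to pioglitazone, and the documents do not support using it as a pioglitazone effect size or prior. This follows from the shared start in Study Week 0 and the time-only model, and needs no assumption about how well the education works.

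The size of the misattribution is unknown. Under assumed education effects of 5-20% and no other influence, a total rate ratio of 0.80 is compatible with a drug rate ratio from 0.84 to 1.00. The rejection rates in the working are illustrations that depend on the assumed effect, on weekly drinks as the outcome and on the variance; version (a) also rests on the unreproduced 80% power figure. The missing education record is a separate, minor gap that is easily closed.

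**What to change.** 1. Reconcile the placebo wording in Overall study design and Table 1 with the within-subject plan. If there is a concurrent placebo group, describe the allocation, add treatment and treatment-by-time terms, and rest drug conclusions on the treatment-by-time term. N would then need to be re-derived. For a 10:10 split and a 20% drug effect on the difference in change (one-sided 0.05, one baseline week, four follow-up weeks, 10.5 drinks/week, Poisson variance, no education effect), the variance is 2/105 + 1/420 + 1/336 = 0.0244, so power is Φ(0.223/0.156 − 1.645) = 41%. With overdispersion of 2 it is about 26%.
2. If there is no placebo group, state in Aim 2, Hypothesis 2 and the power section that the estimate is uncontrolled change during pioglitazone given with alcohol education and weekly monitoring. Do not carry it forward as a pioglitazone-only effect size or prior.
3. In either case, collect the Week 0 outcome measures before the first pamphlet review and log each education session by visit, so that exposure can be described. Leave the offer of repeat sessions to the investigators.

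Without a placebo group, the cost is protocol wording, one case report form line and a more modest Aim 2 conclusion. The sample size and the education itself stay as they are.
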